Appendix C (The IRB-approved Protocol)

The National Health and Nutrition Examination Survey (NHANES)

The National Health Interview Survey (NHIS)

The Behavioral Risk Factor Surveillance System (BRFSS)

The Current Population Survey (CPS)

The American Healthy Homes Survey (AHHS)

The American Housing Survey (AHS)

Results from the research studies have been extensively published in peer-reviewed environmental health journals that provided scientific basis for home-based asthma intervention studies (Wilson et al., 2009). Some questions from these studies were included verbatim in the Green Housing Study baseline questionnaire, some were modified to fit our study framework, and some additional questions were added (Table 24). CDC epidemiologists modified some of the existing questions and developed new questions in consultation with academic peers and subject matter experts.

Appendix C (The IRB-approved Protocol)

Table 24. Examples of questions used in the Green Housing Study and their provenance.

Questions	Questionnaire Type	Question	Name of the study	Reference article
Included verbatim	Baseline (Home characteristics)	In the last 3 days: today or yesterday or the day before yesterday, have you either breathed fumes from gasoline or had it on your skin?	NHANES	n/a
	Baseline (Child with asthma age 7-12)	Is [Child's name] currently covered by any kind of health insurance or some other health care plan?	NCS	n/a
	Illness checklist	Did you receive Tamiflu® or oseltamivir [o sel TAM i veer] or an inhaled medicine called Relenza® or zanamivir [za NA mi veer] to treat this illness?	BRFSS	n/a
Included with minor modifications	6 and 12 month follow-up (Child with asthma age 7-12) * note: the mother or primary caregiver answers this question, not the child.	Green Housing Study version: In the last 3 months, did [Child's name] receive Tamiflu® or oseltamivir [o sel TAM i veer] or an inhaled medicine called Relenza® or zanamivir [za NA mi veer] to treat this illness? BRFSS version: Last month, did you receive Tamiflu® or oseltamivir [o sel TAM i veer] or an inhaled medicine called Relenza® or zanamivir [za NA mi veer] to treat this illness?	BRFSS And also recent H1N1 flu pandemic surveillance	Cauchemez S, Donnelly CA, Reed C, Ghani AC, Fraser C, Kent CK, Finelli L, Ferguson NM. Household transmission of 2009 pandemic influenza A (H1N1) virus in the United States. N Engl J Med. 2009 Dec 31;361(27):2619-27.

After development of initial draft, the baseline questionnaire was distributed among CDC, NIH, EPA, and HUD colleagues and five non-federal academic peers (Drs. [name], [name], [name], [name], and [name]) for face and content validation. Based on repeated feedback received from peers, the questionnaire underwent multiple revisions before a final draft was prepared. Cognitive interviews with nine or fewer college-educated CDC colleagues were conducted in a controlled environment. The questionnaire underwent a final revision based on the responses from participants. Some of the results from this pilot testing are shown below.

Appendix C (The IRB-approved Protocol)

Each of the questionnaires was pilot-tested at CDC on nine or fewer (in some cases not all 9 were available to participate) predominantly college-educated CDC employee-volunteers during non-work hours. The pilot tests were administered by two Green Housing Study researchers. The results of our pilot testing are shown in Table 25. Based upon pilot testing, the questionnaires were revised to increase ease of understanding and speed of response. We conservatively estimated the response times for our study participants (low-income mothers/primary caregivers living in multifamily, urban housing) based on the average response times recorded during our pilot tests.

Table 25. Pilot test of each questionnaire and estimated response time for study participants

Form name	Average response time (minutes)	Minimum response time (minutes)	Maximum response time (minutes)	Estimated response time for study participants
Screening questionnaire	4:52	2:16	7:57	10
Baseline Questionnaire (Home Characteristics)	6:03	4:37	7:15	15
Baseline Questionnaire (Part 2: Home Characteristics)	2:56	2:26	3:31	5
Baseline Questionnaire (Mother/primary caregiver)	0:58	0:50	1:15	5
Baseline Questionnaire (for Children with asthma 7-12 years)	6:38	6:20	6:50	15
3 and 9-month Phone contact	2:30	2:15	2:45	5
6 and 12-month Follow-up Questionnaire (for environment)	3:52	3:10	4:20	10
6 and 12-month Follow-up Questionnaire (for children with asthma 7-12)	3:07	3:00	3:15	10
Time/Activity form (for Mothers/primary caregivers of enrolled children)	1:45	1:40	2:00	5
Time/Activity form (for Children with asthma 7-12 yrs)	0:40	0:35	0:50	5
Illness Checklist	1:05	0:45	1:25	5

B.5. Individuals Consulted on Statistical Aspects and Individuals Collecting and/or Analyzing Data

Appendix C (The IRB-approved Protocol)

APPENDIX B

Table B-1 lists additional chemicals and media. Should resources allow, media will be analyzed for additional chemicals as shown in the table.

Appendix C (The IRB-approved Protocol)

Table B-1. Additional chemical and biological agents to be considered if resources allow for the EPA pilot study add-on.

Target Compound Class	Target Chemical/Biological	Media	Biomarkers	
Consumer Product Active Ingredients	2-Butoxyethanol	Indoor air, dust, surface wipe, hand wipe, duplicate diet, urine, blood, soil	2-butoxyacetic acid (and conjugate)	
	Linalool	Soil, hand wipe, blood	_ ^a	
	Limonene	Soil, hand wipe, blood	_ ^a	
	Pinene	Indoor air, dust, surface wipe, hand wipe, duplicate diet, urine, blood, soil	_ ^a	
	Diethanolamine	Indoor air, dust, surface wipe, hand wipe, duplicate diet, urine, blood, soil	_ ^a	
	Monoethanolamine	Indoor air, dust, surface wipe, hand wipe, duplicate diet, urine, blood, soil	_ ^a	
	Methyl paraben	Soil, hand wipe, blood	Methyl paraben conjugates, p -hydroxybenzoic acid and conjugates	
	Propyl paraben	Soil, hand wipe, blood	Propyl paraben conjugates, p -hydroxybenzoic acid and conjugates	
	Butyl paraben	Soil, hand wipe, blood	Butyl paraben conjugates, p -hydroxybenzoic acid and conjugates	
	Methoxypropanol	Indoor air, dust, surface wipe, hand wipe, duplicate diet, urine, blood, soil	_ ^a	
	Triclosan	Indoor air, hand wipe, duplicate diet, blood, urine, soil	Triclosan conjugates, 2,4-dichlorophenol (2,4-DCP)	
	BPA and Replacement Chemicals	BPA	All media ^b	BPA glucuronide, sulfate conjugates
		BPS	All media ^b	_ ^a
BPP		All media ^b	_ ^a	
BPF		All media ^b	_ ^a	
BPB		All media ^b	_ ^a	
BPZ		All media ^b	_ ^a	
Flame Retardants	PBDEs	BDE47	All media ^b	_ ^a
		BDE99	All media ^b	_ ^a
		BDE100	All media ^b	_ ^a
		BDE153	All media ^b	_ ^a
	OPs	TCPP	All media ^b	_ ^a

Appendix C (The IRB-approved Protocol)

	TCEP	All media ^b	- ^a		
	TDCPP	All media ^b	- ^a		
	TPP	All media ^b	- ^a		
Pesticides	OCs	Chlordane	All media ^b	Oxychlordane	
		DDT	All media ^b	DDD, DDE	
		Endosulfan	All media ^b	Endosulfan sulfate, endosulfan ether, endosulfan lactone	
		Pentachlorophenol	All media ^b	TCHQ	
		Acephate	All media ^b	- ^a	
	OPs	Dichlorvos (DDVP)	All media ^b	Dichloroacetaldehyde, dichloroacetic acid	
		Malathion	All media ^b	Malaoxon DCA, malathion MCA, o,o-DMPT, DEDTP, o,o-DMDTP, o,o-DMP, 2-[(dimethoxyphosphorothioyl) sulfanyl] succinic acid (malathion dicarboxylic acid)	
		Pyrethroids	TCVP (Tetrachlorovinphos)	All media ^b	DMP
			Trichlorfon	All media ^b	Dichlorvos
			Allethrin	All media ^b	- ^a
	Bifenthrin		All media ^b	2-methyl-3-phenylbenzoic acid (MPA)	
	Pyrethroids	Cyfluthrin	All media ^b	4F-3PBA, cis/trans -DCCA	
		Lambda -Cyhalothrin	All media ^b	3-PBA, 3-PBA glucuronide/glycine conjugates	
		Cypermethrin	All media ^b	3-PBA, 3-PBA glucuronide/glycine conjugates, cis/trans -DCCA	
		Cyphenothrin	All media ^b	3-PBA, 3-PBA glucuronide/glycine conjugates	
Deltamethrin		All media ^b	4'-OH deltamethrin, cis/trans -DBCA, cis/trans -DBCA glycine, cis/trans -DBCA glucuronide		
Esfenvalerate		All media ^b	3-PBA, 3-PBA glucuronide/glycine conjugates		
Imiprothrin		All media ^b	- ^a		
Metofluthrin		All media ^b	HOCH ₂ -FB-Al, MCA, CH ₃ OCH ₂ -FB-Al		
Prallethrin		All media ^b	- ^a		
Pyrethrins		All media ^b	trans -chrysanthemum dicarboxylic acid (CDCA)		

Appendix C (The IRB-approved Protocol)

		Resmethrin	All media ^b	- ^a
		Tetramethrin	All media ^b	- ^a
		Tralomethrin	All media ^b	- ^a
		Aldicarb	All media ^b	Aldicarb sulfoxide
	Carbamates	Carbaryl	All media ^b	1-naphthol + sulfate /glucuronide conjugates, 4-(Hydroxy)-1-naphthyl N-methyl carbamate + glucuronide conjugate
		Propoxur	All media ^b	- ^a
	Juvenile Hormone Analog	Pyriproxyfen	All media ^b	- ^a
	Pediculicide	Spinosad	All media ^b	- ^a
	Trifluoromethyl aminohydrazone	Hydramethylnon	All media ^b	- ^a
		2,4-D	All media ^b	2,4-dichlorophenol (2,4-DCP)
	Herbicides	Atrazine	All media ^b	- ^a
		Bensulide	All media ^b	- ^a
		Dicamba	All media ^b	- ^a
	Amidine insecticide	Glyphosate Amine	All media ^b	- ^a
		Amitraz	All media ^b	- ^a
	Neonicitinoids	Imidacloprid	All media ^b	6-chloronicotinic acid
		Thiamethoxam	All media ^b	- ^a
	Insect Growth Regulators	Azadirachtin	All media ^b	- ^a
		Novaluron	All media ^b	- ^a
Perfluorinated Compounds		C4 – C14 carboxylic acids	Dust, soil, hand wipe, blood	- ^a
		PFOS	Dust, soil, hand wipe, blood	- ^a
		PFBS	Dust, soil, hand wipe, blood	- ^a
		PFHS	Dust, soil, hand wipe, blood	- ^a
		PFDS	Dust, soil, hand wipe, blood	- ^a
Metals		Aluminum	Socks	- ^a
		Arsenic	Socks	- ^a
		Cadmium	Socks	- ^a
		Silicon	Socks	- ^a
		Titanium	Socks	- ^a
General Biomarkers				acetylcholinesterase (AChE), butyrylcholinesterase, leukotrienes, cortisol, cytokines, creatinine
Untargeted analyses			Dust, duplicate diet, urine	

^aDenotes biomarker is parent compound.

Appendix C (The IRB-approved Protocol)

^bSee Table 4 for a complete list of media.

Appendix C (The IRB-approved Protocol)

APPENDIX C

Location, Transportation, Activity, Diet, Consumer Products, and Home Observation
Questionnaire (CDC IRB Approved, IRB#5587, April 2013)

Appendix C (The IRB-approved Protocol)

Household ID#

Child's Age

Child's Gender

F

M

Date

Interviewer's Initials

A. Introductory Questions (To be completed by field technician and participant)

1. Has your child been diagnosed with asthma by a doctor?

Yes

No

Don't Know/Refused to answer

2. Did your child experience any asthma symptoms yesterday (e.g., wheezing, shortness of breath, tightness in chest, dry cough)?

Yes

No

Don't Know/Refused to answer

Appendix C (The IRB-approved Protocol)

B. Location Questions (To be completed by field technician and participant)

3. For each approximate time period given below, indicate where your child was located. Select any locations that apply to the time period.

	Home	Outdoor area at home	Other residence (ex. babysitter's house)	Store	Restaurant	Church	Other indoor location	Park	Bus/train stop	On or near street	Parking garage	Other outdoor location	In vehicle	Don't know/Refused to answer
5:00 am - 5:29 am														
5:30 am - 5:59 am														
6:00 am - 6:29 am														
6:30 am - 6:59 am														
7:00 am - 7:29 am														
7:30 am - 7:59 am														
8:00 am - 8:29 am														
8:30 am - 8:59 am														
9:00 am - 9:29 am														
9:30 am - 9:59 am														

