Appendix C (The IRB-approved Protocol)

4.5 Questionnaire

One questionnaire will query participants on location, transportation, activity, diet, and consumer products use and will be used by the field staff to record home observations (Appendix C). It will complement the questionnaires currently being used in the Green Housing Study and will be administered using a conventional pen and paper approach to the mother/caregiver for the index child and participating sibling(s). The questionnaire is primarily a recall questionnaire covering the activities of the index child and sibling(s) on the day prior to each field visit. Figure 2 shows the data flow for the questionnaire.

Figure 2.

Questions will gather information on the types of locations the children visited throughout the day, including residences, non-residential indoor environments (e.g., schools and stores), and outdoor environments. In order to reduce burden, questions will be asked about the 5 locations where each child spent the most total time. A series of transportation questions will also be asked related to how the children moved from one location to another to characterize time spent in vehicles or other near-road locations (e.g., street or bus stop). Questions will also ask about the types of activities performed in each location, with a primary focus on activities relevant to exposure to consumer products (e.g., bathing or grooming activities, chores, and contact with pets); however, other general categories of activities are included for estimating an overall level of energy expenditure for each child relevant to intake dose rates of indoor chemicals.

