Activity and location data will be aggregated into an electronic database and further processed by EPA investigators into a format consistent with EPA's Consolidated Human Activity Database (CHAD; McCurdy et al., 2000, U.S. EPA, 2002). This format includes demographic, date, and housing information linked with a minute-by-minute diary of location and activity for the individual studied. It is anticipated that if the data quality from the questionnaires are adequate, these time activity data (de-identified) would be permanently entered in CHAD for use by EPA exposure models (and available to the public via download).

Understanding the type, magnitude, and variability of time spent in microenvironments across ages, geographic region, subculture, or socioeconomic status is critical in performing exposure assessments for different populations of children. Therefore, time spent in each microenvironment by each child will be summarized by standard methods (for example, Xue et al., 2004). Of specific interest will be differences in time spent in locations for children of different ages in the same household. Additionally, location information will be combined with

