Appendix C (The IRB-approved Protocol)

house dust loading measurements or personal samples in order to model children's soil and dust ingestion rates (objective 10). Finally, the interaction of time spent in different locations with housing and community factors such as crime rate, transportation options, and perception of children's safety will be quantified.

From the activity survey results, descriptive statistics of reported time spent in microenvironments and activities will be calculated. In addition, GPS-based time spent in microenvironments will be calculated using EPA's MicroTrac model (Breen et al., 2014). This model takes as input a GPS time-series and a general location of the participant's home and using a computational algorithm calculates time spent at home and in travel (in vehicles). The MicroTrac results will be compared with the survey results as in Breen et al. (2014). Differences among age groups, genders, and asthmatic/non-asthmatic children for both survey and GPS results will be quantified and tested using appropriate parametric or non-parametric techniques.

Children's activities are an important determinant of the types and amounts of chemicals encountered (McCurdy, 2000). Therefore, time spent in exposure-relevant activities (e.g., time spent with pet or exercising) will be characterized via standard methods (Xue et al., 2004). A primary analysis will evaluate age- and asthma-dependent differences in activity level in children living in the same household. The results from this analysis will aid in characterizing/elucidating the contributions of age, health, socioeconomic status, and other factors to describe the variability in activity levels. Similar to location, the interaction between housing and community factors (e.g., crime or noise pollution) and exposure relevant activities will be addressed. In addition, the location of high-dose rate activities (e.g., exercise) for these children will be compared to other, previously studied child cohorts to assess the influence of community or socioeconomic status-driven factors (such as distance from pollutant sources, or indoor versus outdoor exercise locations).

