Appendix C (The IRB-approved Protocol)

	Home	Outdoor area at home	Other residence (ex. babysitter's house)	Store	Restaurant	Church	Other indoor location	Park	Bus/train stop	On or near street	Parking garage	Other outdoor location	In vehicle	Don't know/Refused to answer
9:00 pm - 9:29 pm														
9:30 pm - 9:59 pm														
10:00 pm - 10:29 pm														
10:30 pm - 10:59 pm														
11:00 pm - 11:29 pm														
11:30 pm - 11:59 pm														

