Appendix C (The IRB-approved Protocol)

C. Activity Questions (To be completed by field technician and participant)

5. For each approximate time period given below, indicate activities your child performed. Select all that apply for the time period.

	Dress, groom or bathe	Eat	Watch TV	Play	Use computer or play video games	Read or do school work	Take care of younger children	Chores	Exercise	Play with pet	Arts and crafts	Sleep	Don't know/Refused to answer	None of these
5:00 am - 5:29 am														
5:30 am - 5:59 am														
6:00 am - 6:29 am														
6:30 am - 6:59 am														
7:00 am - 7:29 am														

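### The half-hour location grid records presence and not minutes, so Objective 8's short-stay totals, diary and GPS comparison depend on an unstated allocation rule

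*Protocol*

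**What the plan says.** **The form.** Item 3 of the questionnaire lists half-hour rows from 5:00 am to a last row of "11:30 pm - 11:59 pm", with the instruction "Select any locations that apply to the time period". The columns include home, other residence, street, bus or train stop, parking garage and vehicle. No minutes and no order are asked for.

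**The use.** Section 5.0, Objective 8, says that "time spent in each microenvironment by each child will be summarized by standard methods". It also says that, from the survey, "descriptive statistics of reported time spent in microenvironments and activities will be calculated", and that the data will be put into a database format with a "minute-by-minute diary of location and activity for the individual studied". Table 8 specifies a paired t-test and correlations between questionnaire and GPS location results. The GPS model returns time at home and time in vehicles. Section 4.4.4 makes the last day of device wear (Day 4) the day that the questionnaire asks about.

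**The promised items.** Section 4.5 says that "questions will be asked about the 5 locations where each child spent the most total time", and announces a series of transportation questions to characterize time in vehicles and near roads.

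**The concern.** The form captures whether a child was somewhere during a half hour. The analysis needs to know for how long. A short car ride can put ticks on home, vehicle and destination in one row, and nothing on the form says how the 30 minutes divide among them.

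A statistical analysis plan could supply a rule for dividing rows, but it cannot recover durations that were never collected. Vehicle time is one of the two quantities that the GPS model returns. A difference between questionnaire and GPS minutes would therefore mix recall error with the effect of the dividing rule, and the t-test could not separate them. The same rule would shape the time-spent summaries and any diary record built from the form.

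**Working it through.** **1. Is duration recoverable from another item?** The form runs from section A to section J with items numbered 1 to 31 without a gap. Transportation is in its title, but there is no transportation section and no question about the five main locations. The only durations are usual-day bands (floor time, and play outdoors at home, at school or daycare, and at local parks: items 8 and 10 to 12). None concerns vehicles or the recalled day.

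**2. Coverage.** 5:00 am to midnight is 19 h × 2 = 38 rows, and 38 × 30 = 1,140 min.

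**3. Size.** The protocol states no time total and no crediting rule, so there is no figure to reproduce. Assumptions: a trip of L = 10 or 15 min, starting at any whole minute of a row with equal chance, between two different places, with perfect recall.

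*Rule A, 30 min per tick.* Of 30 possible starts, L − 1 cross into a second row, so the vehicle is credited with 30 × (1 + (L − 1)/30) min:
- L = 10: 30 × 1.30 = 39 min, or 3.9×.
- L = 15: 30 × 44/30 = 44 min, or 2.9×.

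*Rule B, row divided equally among ticked places.* A trip strictly inside a row shares it three ways (10 min). A trip touching a row edge shares it two ways (15 min). A crossing trip gets half of each of two rows (30 min):
- L = 10: (19 × 10 + 2 × 15 + 9 × 30)/30 = 490/30 = 16.3 min, or 1.6×.
- L = 15: (14 × 10 + 2 × 15 + 14 × 30)/30 = 590/30 = 19.7 min, or 1.3×.

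| Day (assumed) | True vehicle min | Rule A | Rule B |
|---|---|---|---|
| Two 10-min trips | 20 | 78 | 32.7 |
| Two 15-min trips | 30 | 88 | 39.3 |
| Four 15-min trips | 60 | 176 | 78.7 |

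With perfect recall and perfect GPS, the paired difference for two 10-minute trips would be +58 min under A and about +13 min under B. That gap comes from the rule alone.

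**4. Sensitivity.** With a continuous random start, Rule A inflates by 1 + 30/L: 7× at 5 min, 4× at 10, 3× at 15, 2× at 30 and 1.5× at 60. If only one other place shares the row, equal division gives 3.5× at 5 min, 2.0× at 10, 1.5× at 15 and 1.0× from 30 min up. The direction is not fixed for a single stay: a 20-minute stay inside one row shared with one other place is credited 15 min, or 0.75×.

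**5. Row totals under Rule A.** A trip adds two extra ticks for 28 of the 30 starts and one for the other two: 58/30 × 30 = 58 min. Two trips give 1,140 + 116 = 1,256 min (20.9 h), and four give 1,372 min (22.9 h). Both exceed the 19 h covered but not 24 h. Passing 24 h takes 11 extra ticks (1,140 + 330 = 1,470 min). Under Rule B every row sums to 30 min and the total stays at 19 h.

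**The case against.** The strongest reply is that the protocol never says a tick counts as 30 minutes. Objective 8 has investigators process the answers before they enter the diary format, and a coding rule for rows with several ticks is commonly left to the analysis plan or data-management documents, which are not shown. Trip lengths are also not in the protocol. All of this stands, and it is why the sizes above are conditional.

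A reader might infer several stronger points that the documents do not support:
- *Totals exceed the day.* This needs 30 minutes per tick, and even then the worked examples stay under 24 h.
- *Short stays are inflated two- to four-fold as a matter of fact.* That holds only for particular assumed lengths under that same rule.
- *The activity grid (item 5) has the same fault.* Its instruction is "Select all that apply for the time period", but a child can eat and watch television at once, so activity minutes above clock time can be genuine.
- *Inflated times will enter the public database.* A diary with one location per minute cannot exceed the period covered, and entry depends on adequate data quality. The risk there is arbitrary allocation.
- *The GPS comparison fails.* A vehicle offset could be detected in it, and home time should be affected much less in proportion.

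The quality condition is only partial protection. The survey checks under Objective 2 (completeness above 90%, comprehension, range of responses) can all be met by a fully completed multi-tick grid. The remaining check, against GPS, covers home and vehicle only and is itself altered by the dividing rule. The parent study also has a Time/Activity form, but its content is not shown, and it is listed for the index child and caregiver and not for siblings.

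**Conclusion.** The mismatch is real. The location grid yields presence by half hour, Objective 8 treats it as a source of minutes, and the items in Section 4.5 that could have closed the gap are absent from the form. Vehicle and other short-stay totals therefore depend on an arbitrary allocation rule. For assumed trips of 10 to 15 minutes at random start, the overstatement is about three- to four-fold at 30 minutes per tick, with totals above the 19 h covered. It is about 1.3 to 1.6 times under equal division for trips between two different places. These sizes rest on assumed trip lengths, crediting rules and perfect recall. This should be corrected. It affects Objective 8 and the survey-quality comparison under Objective 2, and it does not touch the environmental or biological measurements.

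**What to change.** 1. **GPS comparison.** Convert the Day 4 GPS output to the same half-hour any-presence indicators for home and for vehicle, and compare row by row in place of the paired t-test on minutes. This needs no new data, provided that the time-stamped GPS classification is kept.
2. **Form.** Reconcile Section 4.5 with the questionnaire by restoring the transportation items, including minutes in vehicle per trip, and the time in the five main locations. Keep the multi-tick grid: allowing only one main place per row would erase the short stays at streets and bus stops that Section 4.5 wants to capture.
3. **Time totals and diary.** Fix one allocation rule that makes each location row sum to 30 minutes, and report the totals over a range of alternative rules.

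The cost is a form amendment, with the reviews that Section 7.2 requires for the questionnaire, and a little more caregiver time. If forms are already in use, steps 1 and 3 still apply to the data collected.
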